# 8.4.1 Biomarkers

Blood samples for DNA and RNA isolation will be collected from all patients. Analysis of DNA and RNA isolated from blood will include, but is not limited to, analysis of the T cell receptor repertoire, analysis of circulating tumor DNA, and analysis of microRNAs. Blood samples may be also used to isolate and analyze circulating tumor cells.

Blood samples will be stored, and analysis may be performed on biomarker variants thought to underlie the interplay between immune activation provoked by vaccination with UV1 and inhibition of tumor resistance mechanisms and peripheral immune tolerance induced by checkpoint blockade. Analyses may include but are not limited to levels of antibodies specific for vaccine peptides, tumor-specific antigens, cytokines, chemokines, and inflammatory factors. Assessments of potential biomarkers may be used to evaluate their association with observed clinical responses to UV1 vaccination in combination with nivolumab and ipilimumab, or nivolumab and ipilimumab alone.

The final disposition of samples will be conducted per local regulations.

Samples may be stored for a maximum of 5 years (or according to local regulations) following the last patient's last visit for the study at a facility selected by the Sponsor to enable further analysis of biomarker responses.

## 8.5 Extended Exploratory Cohort

A cohort of approximately 40 patients at selected sites will be asked to volunteer for additional biological sampling and analysis. Extended blood sampling, tumor biopsy collection, fecal sampling, and DTH testing (only for experimental arm) will be conducted on patients in the Extended Exploratory Cohort. Exploratory assessments related to the biological samples collected from this cohort of patients with rationale and objectives are described in Appendix 2. The samples collected in the Extended Exploratory Cohort will be in addition to those required elsewhere per protocol for all patients.

## 8.6 Single Arm UV1 Cohort

To support the Extended Exploratory Cohort of the study, an additional 20 patients at selected sites will be enrolled in a single arm UV1 cohort for collection of additional biological material. (Appendix 7).

# 9 Statistical Methods

The statistical considerations summarized in this section outline the plan for data analysis of this study. Any deviations from the planned analyses will be described in the Statistical Analysis Plan and justified in the final integrated study report.

## 9.1 Statistical Hypothesis

The primary endpoint is PFS. Under the null hypothesis, the PFS HR for UV1 vaccination in combination with nivolumab and ipilimumab versus nivolumab and ipilimumab is assumed to be unity. Under the alternative hypothesis, the PFS HR is assumed to be 0.60 or better, representing a beneficial effect on PFS for UV1 vaccination in combination with nivolumab and ipilimumab compared to nivolumab and ipilimumab.

## 9.2 Sample Size Determination

To test the PFS null hypothesis with 80% power and a 1-sided alpha level of 0.10, a total of 70 PFS events are required. Hodi et al  $(2018)^{14}$  provides data on PFS with nivolumab and ipilimumab in patients with advanced melanoma. Assuming a similar shape of the PFS curve for nivolumab and ipilimumab is observed in the current study, 154 patients randomized over a 15-month period and followed thereafter for a minimum of 12 months will give a mean follow-up of PFS events of approximately 20 months. Follow-up for survival will continue for an additional 24 months after the PFS analysis at which time 60 deaths are expected to have accrued; this many deaths, an observed OS HR of 0.60 would reach p<0.025 1-sided.

As of 19 September 2023, blinded event accrual stood at 63 PFS events. A blinded examination of the overall PFS Kaplan Meier curve made as of 23 July 2023, and then repeated as of 19 September 2023, showed strong evidence for a plateau at 54 to 55% of subjects alive and without progression. Such a PFS curve plateau is not uncommon for IO therapies. In CheckMate 67, nivolumab plus ipilimumab, nivolumab alone and ipilimumab alone were evaluated in advanced melanoma (Hodi 2018). This study formed the basis of the sample size calculations for the current study and showed a prolonged PFS tail for nivolumab plus ipilimumab plateauing at approximately 40% for subjects alive and without progression. However, the blinded data realized thus far has shown a higher plateau at 54 to 55% for subjects alive and without progression.

Specifically, there seems to be very little contribution to PFS events after 18 months in the study, with the PFS curve nearing asymptote. The plateau in the current study commences at approximately 21 months post first subject randomized with an estimated 56.02% of subjects alive and without progression and persists thereafter for 15 months, out to 36 months at which time 54.32% subjects are alive and without progression, i.e. an increase in the progression rate of only 1.7% over 15 months. Based on the projected PFS curve, 70 PFS events are not expected to be reached by late 2028 at which time 69.3 events, 90% CI of (69.2, 72.3), are expected.

Given the observed plateau in the accrual of PFS events, it has been decided to execute the primary analysis of PFS at the earliest of either 70 PFS events reached across both treatment

arms or 18 months post last patient randomized. An analysis with slightly fewer PFS events has negligible impact on the observed HR to reach a given level of statistical significance.

# 9.3 Analysis Populations

Analysis populations	Description
Intention-to-treat (ITT)	All randomized patients. Efficacy data in this population will be
population	summarized by randomized treatment. The primary PFS and secondary
	OS analysis will be assessed in the ITT population. Patients will be
	analyzed by the treatment arm to which they are randomized.
Response evaluable	All randomized patients with measurable disease by RECIST 1.1. The
population	secondary endpoint analyses of ORR and DOR will be assessed using
	the response evaluable population. Patients will be analyzed by the
	treatment arm to which they are randomized.
Safety population	All randomized patients who receive at least one dose (or partial dose)
	of induction therapy. Patients will be assessed by the treatment
	received, based on the first dose of study drug.

For purposes of analysis, the following analysis populations are defined:

## 9.4 Statistical Analysis

## 9.4.1 General Considerations

Demographic data and disease-related baseline characteristics will be summarized using descriptive statistics (count and percent, mean, median, standard deviation, minimum, and maximum). All patient, efficacy, and safety data will be summarized. In addition to the summarized analysis plan outlined below, a Statistical Analysis Plan (SAP) will be written and finalized prior to the first planned data analysis. The SAP will provide a detailed and expanded description of the statistical methods outlined in this protocol. Additional analyses, such as in important subgroups, will also be described in the SAP.

# 9.4.2 Efficacy Analyses

# 9.4.2.1 Primary Efficacy Analyses

#### Progression Free Survival

Progression free survival is defined as time from randomization to progression (by BICR) or death from any cause, whichever occurs first. A Cox proportional hazards regression model will be used to analyze PFS on an ITT basis. Patients who have not progressed or died will be censored at their last follow-up tumor assessment. The model will include a single covariate for randomized treatment and covariates for baseline ECOG (0 versus 1) score. The HR will be estimated from the model along with the associated 2-sided CI and 2-sided p-value. The data will also be displayed using Kaplan-Meier curves and median PFS times will be estimated. The PFS
at 12 months will be estimated from the Kaplan-Meier curves along with the associated 80% and 95% Cis.

#### Sensitivity Analyses of the Progression Free Survival

Several sensitivity analyses will be performed on the primary endpoint:

- i. As per FDA guidance, a sensitivity analysis will be performed in patients who started any subsequent anticancer treatment without a prior reported progression. Patients will be censored at the last evaluable tumor assessment prior to initiation of the subsequent anticancer treatment; and
- ii. A log rank test on PFS as determined by BICR. The 2-sided p-value will be extracted and presented alongside the results of the Cox analysis; and
- iii. A Cox regression analysis on PFS as determined by the local Investigator's review; and
- iv. A log rank test on PFS as determined by the local Investigator's review. The 2-sided p-value will be extracted and presented alongside the results of the Cox analysis.

Additional sensitivity analyses may be specified in the SAP.

### 9.4.2.2 Secondary Efficacy Analyses

#### **Overall Survival**

Overall survival is defined as the time from randomization to death from any cause. Overall survival will be analyzed in a fashion similar to that described for PFS. Overall survival data at the time of the PFS analysis and with an additional follow-up thereafter will be analyzed until defined end of study to provide evidence supportive of PFS.

#### **Objective Response Rate**

Objective response rate is defined as the proportion of patients with a best response of CR or PR (by BICR). The ORR will be analyzed by exact logistic regression. The model will include a single covariate for randomized treatment and covariates for baseline ECOG (0 versus 1) score. The exact odds ratio will be estimated from the model along with the associated 80% and 95% Cis and 2-sided p-value. Exact Clopper-Pearson 2-sided 80% and 95% confidence limits will be calculated for the proportion of patients with ORR in each arm.

#### Duration of Response

Duration of response is defined as the time from first CR or PR (by BICR), whichever is recorded first, to progression (by BICR) or death from any cause, whichever occurs first. The DOR will be analyzed via Cox regression modelling with a fixed effect term for randomized treatment. The HR will be estimated from the model along with the associated 80% and 95% CI and 2-sided p-value. The data will also be displayed using Kaplan-Meier curves; median DOR and the 80% and 95% Cis will be estimated from the Kaplan-Meier curve by treatment arm. Since DOR is assessed in responding patients only, a supportive analysis will be performed

based on the expected duration of response as per Ellis et al  $(2008)^{32}$  as this analysis includes all randomized patients, including those who did not respond.

## 9.4.3 Safety Analyses

Adverse events will be classified using the latest version of the Medical Dictionary for Regulatory Activities (MedDRA) classification system. Treatment-emergent AEs (TEAEs) will be summarized. A TEAE is defined as an AE that was not present prior to first study treatment but appeared following treatment, or was present at treatment initiation but worsened during treatment. An AE that was present at treatment initiation but resolved and then reappeared while the patient was on treatment is a TEAE (regardless of the intensity of the AE when the treatment was initiated). For simplicity, TEAEs will be referred to as AEs in this protocol. Adverse events will be summarized descriptively by treatment arm, in terms of body system and MedDRA preferred term. Patients with multiple occurrences of the same AE will only be counted once at the maximum severity/grade for each preferred term, system organ class, and overall. Adverse events will be summarized in terms of the number and percentages of patients experiencing related AEs, SAEs, AEs leading to dose interruption, AEs leading to withdrawal from randomized treatment, and AEs leading to death. In the event that a patient experiences repeated episodes of the same AE, the patient will be counted once within each system organ class and similarly counted once within each preferred term and the event with the highest severity grade and/or strongest causal relationship to each treatment will be used for incidence tabulations.

Laboratory values and change from Baseline will be summarized using descriptive statistics at scheduled visits by treatment. Shift tables of the worst on-study laboratory toxicity relative to Baseline will be presented by treatment arm. Patient listings of Grades  $\geq$ 3 laboratory toxicities will be provided.

Vital signs and ECOG performance status (observed and change from Baseline) will be summarized using descriptive statistics by timepoint and treatment.

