From signing of the Informed Consent Form (ICF) until the first dose of induction therapy, only AEs/SAEs caused by study-specific procedures should be reported. Non-serious AEs should be reported from the first dose of induction therapy until 30 days after the last dose of induction therapy, or until new anticancer treatment is initiated (whichever comes first). All SAEs should be reported from the first dose of induction therapy until 70 PFS events are reached, until 18 months post last patient randomized or until new anticancer treatment is initiated (whichever comes first). Adverse events and SAEs that are ongoing beyond the required reporting timelines shall be followed up locally per institutional practice until resolution or stabilization or the patient is lost to follow up.

During the study, an Independent Data Monitoring Committee (IDMC) will monitor safety information to ensure patient safety (refer Section 8.2.1).

Patients at selected sites will have the option to be included in the Extended Exploratory Cohort of the study (Appendix 2) provided that the cohort is still open for inclusion. This cohort of approximately 40 patients, randomized in a 1:1 ratio to either of the 2 treatment arms, will have additional sampling of blood, tissue, and feces for exploratory purposes (see Table 9 and Table 10). The biologic sampling will be in addition to blood samples planned for all patients in the study. Fecal samples will be collected in the Screening period while tumor biopsies (snap-frozen tissue and formalin fixated paraffin embedded tissue) will be harvested in the Screening period and at the safety follow-up visit. In the experimental arm, delayed-type hypersensitivity (DTH) response will be assessed at 5 timepoints during the study. A biobank will be established for current and future analysis of the samples collected.

In addition to the 2-armed part of the study, 20 patients will be enrolled in a single arm UV1 cohort for collection of additional biological material to support the Extended Exploratory Cohort of the study. The single arm UV1 cohort is intended for exploratory purposes only (Appendix 7 Single Arm UV1 Cohort).

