# 4.2 Measures to Minimize Bias: Randomization and Blinding

Patients who satisfy all eligibility criteria will be randomly assigned by the central interactive web response system (IWRS; or equivalent) to receive induction therapy as either UV1 vaccination in combination with nivolumab and ipilimumab in the experimental arm, or nivolumab and ipilimumab in the control arm. Randomization will be at a 1:1 ratio between the 2 treatment arms.

Randomization will be done by the IWRS provider using a validated software. Randomization can occur after all Screening procedures have been completed (up to 3 days [from Day -3 until Day 1] prior to first dosing on Day 1) and eligibility has been confirmed, to prevent the Investigator's knowledge of treatment allocation influencing the decision to include the patient.

Given the study design, with visits occurring at different timepoints in the 2 treatment arms, neither patients nor Investigators will be blinded to the study treatment arms. To limit bias in evaluation of the efficacy endpoints, the statistical efficacy analyses will be based on tumor assessments by BICR.

Patients in the single arm UV1 cohort will not be randomized and will therefore not be included in the data used for analysis of primary and secondary endpoints.

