## 7.3.3 Survival Follow-up Visits

Patients who have confirmed iCPD according to iRECIST will continue with survival follow-up visits and be contacted per phone (or, at the investigator's discretion visit the hospital) every 12 weeks for survival status, assessment of SAEs and new anticancer treatments until the earliest of either 70 PFS events reached across both treatment arms or 18 months post last patient randomized.

From the PFS cut-off date is reached, the survival follow-up visits will continue every 6 months for 2 years and only survival status will be collected. Detailed visit instructions will be provided by the sponsor at this time.

The Sponsor may request survival status to be collected at additional timepoints during the study. For example, updated survival status may be requested prior to an IDMC review.

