## 8.3.3 Adverse Event Reporting and Follow-up

# 8.3.3.1 Reporting

Adverse events will be reported by the patient (or, when appropriate, by a caregiver, surrogate, or the patient's legally authorized representative). Care will be taken not to introduce bias when detecting AEs. Open-ended and non-leading verbal questioning of the patient is the preferred method to inquire about AE occurrence (for example, "Have you experienced any new or changed symptoms since we last asked/since your last visit?").

From signing of the ICF until the first dose of induction therapy, only AEs/SAEs caused by study-specific procedures should be reported. All non-serious AEs should be reported from the first dose of induction therapy until 30 days after the last dose of induction therapy, or until new anticancer treatment is initiated (whichever comes first).

All SAEs should be reported from the first dose of induction therapy until 70 PFS events are reached, until 18 months post last patient randomized or until new anticancer treatment is initiated (whichever comes first).

The time periods for reporting of AEs and SAEs are outlined in Figure 4.

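### SAE observation stops at new anticancer treatment, which UV1 is meant to delay, but SAEs are compared only as crude percentages; a time-adjusted SAE summary should be added

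*Combined protocol and SAP*

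**What the plan says.** Comparing safety between arms is a secondary objective (Section 3). Section 9.4.3 describes the summary: "Adverse events will be summarized in terms of the number and percentages of patients experiencing related AEs, SAEs", together with AEs leading to dose interruption, withdrawal or death. The denominator is every randomized patient who received any induction therapy (Section 9.3). No person-time rate, time-to-first-SAE analysis or common observation period for SAEs is specified.

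The collection rules are in Section 8.3.3.1. SAEs are reported from the first induction dose until 70 PFS events are reached, "until 18 months post last patient randomized or until new anticancer treatment is initiated (whichever comes first"). Non-serious AEs have a much shorter window, "until 30 days after the last dose of induction therapy, or until new anticancer treatment is initiated (whichever comes first"). A patient with confirmed progression who has not switched is still observed, since Section 7.3.3 plans contact "every 12 weeks for survival status, assessment of SAEs and new anticancer treatments". It is the switch that closes the SAE window, not progression itself.

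Section 2.7 expects patients to receive further effective anticancer treatment once they progress. Section 9.1 gives the design effect: "Under the alternative hypothesis, the PFS HR is assumed to be 0.60 or better".

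**The concern.** The length of SAE observation is set by a post-randomization event that the experimental treatment is intended to postpone. Early switchers are watched for a few months. Patients who never switch are watched to the cut-off, at least 18 months after randomization if the calendar limit applies. A crude percentage treats both as equally observed.

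If UV1 delays progression, more of its patients remain under SAE observation for longer, and more of them will have an SAE recorded even when the underlying SAE hazard is the same in both arms. Part of any SAE difference would then come from the collection rule and not from toxicity. These tables would feed the benefit/risk assessment of a four-drug combination for which Section 8.2.6 says there are no toxicity data.

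**Working it through.** **Check of the design effect.** Section 9.2 states "To test the PFS null hypothesis with 80% power and a 1-sided alpha level of 0.10, a total of 70 PFS events are required", and Section 4.2 states "Randomization will be at a 1:1 ratio between the 2 treatment arms". Schoenfeld: 4(z₀.₉₀ + z₀.₈₀)² / (ln 0.60)² = 4(1.2816 + 0.8416)² / 0.2609 = 69.1, rounded up to 70. The plan's figure reproduces, so 0.60 is used below. The documents give no SAE rate to reproduce.

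**Step 1: progression-free proportions by arm.** Section 9.2 gives a pooled 56.02% at about 21 months. Solving (s + s^0.6)/2 = 0.5602 gives s = 47.8% for control and s^0.6 = 64.2% for UV1.

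**Step 2: mean SAE window.** Assumptions: follow-up uniform over 18 to 42 months (accrual over about 24 months, from the planned Q2 2020 to H1 2022, then 18 months); PFS hazard constant from the first scan (2.75 months) to 18 months, then none. If every PFS event closes the window:

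mean = 2.75 + 15.25 × (1 − s)/(−ln s) + 12 × s

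- Control: 2.75 + 10.79 + 5.74 = 19.3 months
- UV1: 2.75 + 12.32 + 7.71 = 22.8 months

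If only 60% of PFS events close it, the mean is 0.4 × 30 + 0.6 × the value above: 23.6 and 25.7 months.

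A second model uses a pooled plateau of 55% (46.7% and 63.3% by arm), a smooth approach to the plateau (time constant 4 months) and a switch 1.5 months after progression. It gives 23.3 vs 25.4 months (50% of progressors switch), 19.9 vs 23.1 (75%) and 16.6 vs 20.8 (100%). The difference is therefore about 2 to 4 months.

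**Step 3: crude all-SAE percentage with the same SAE hazard in both arms.** The chance that a first SAE is recorded is ∫ λ(t) S(t) G(t) dt. Here λ is the SAE hazard, S the SAE-free proportion and G the proportion still under SAE observation. Assumed: 30% or 50% of patients have an SAE in the first 4 months, with a constant hazard afterwards, and 60% or 100% of PFS events close the window.

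| Late SAE hazard | Excess in UV1 arm, points |
|---|---|
| 0 | 0.1 |
| 0.5% per month | 0.6 to 1.2 |
| 1% per month | 1.0 to 2.2 |
| 2% per month | 1.6 to 3.7 |
| 3% per month | 2.1 to 4.8 |

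An example from the 2% row is 46.8% vs 50.5%. With a hazard ratio of 1 the excess is 0.

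The second model, at 75% switching, gives late-only SAE percentages (after month 3.2) of 14.8 vs 17.5 at 1% per month and 26.1 vs 30.8 at 2% per month. Section 9.4.3 counts patients with any SAE, so these gaps apply only to patients without an early SAE. Multiplying by 0.7 or 0.5 gives 1.9 or 1.4 points, and 3.3 or 2.4 points. Its extreme corner (all progressors switch, 3% per month, 30% early) gives 28.2 vs 36.5 late-only, and 8.3 × 0.7 = 5.8 points, slightly above the table.

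**Step 4: sampling noise.** With 154/2 = 77 per arm, the standard error of a difference in percentages near 50% is √(2 × 0.5 × 0.5/77) = 8.1 points, and 7.4 near 30%.

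**Step 5: which adjustment works.** For SAEs after month 4 only, at 2% per month with every PFS event closing the window, the crude percentages are 24.4 vs 29.5, but the person-time rate is 24.0 per 100 patient-years in both arms. A single rate pooled over early and late periods fails. With 30% early SAEs, none later and equal hazards, it gives 25.4 (control) vs 21.7 (UV1) per 100 patient-years, a false advantage for UV1.

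**The case against.** The size rests on assumptions. If almost all SAEs occur during induction, the artefact is about 0.1 point. That stands, although Section 7.2.1 warns that immune-related events may appear several months after the last dose, and nivolumab maintenance continues after induction. More SAEs around progression in the control arm could offset the tilt. This is possible, though limited, because Section 8.3.1.2 excludes AEs definitely related to progression.

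The AE summary is descriptive, and no test or decision rule depends on it. Section 9.4.1 leaves further detail to a SAP, so an adjusted summary may yet be planned; no such text is in the documents supplied. Crude incidence also answers a fair question, since patients kept progression-free may receive maintenance for longer. These points support keeping the crude percentages, but none removes the case for showing observation time beside them.

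A reader might also infer that the non-serious AE window is distorted. Section 4.1 runs it "Non-serious AEs should be reported from the first dose of induction therapy until 30 days after the last dose of induction therapy", which for completers is 73 + 30 = Day 103 in the experimental arm and 64 + 30 = Day 94 in control. The schedule does not support that inference. Experimental patients receive UV1 alone until checkpoint therapy starts on Day 10. From the first checkpoint dose to 30 days after the last, the window is 103 − 10 = 93 days against 94 − 1 = 93 days. The 9 extra days are part of the regimen under comparison and are not an artefact of the collection rule.

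**Conclusion.** The point holds for SAEs. Followed as written, the SAE summary is tilted against a UV1 that works. At a PFS hazard ratio of 0.60 with equal SAE hazards, the UV1 arm is observed about 2 to 4 months longer, and its crude all-SAE percentage would tend to be higher by roughly 0 to 5 points. This assumes a late SAE rate of 0 to 3% per month, 50 to 100% of progressors switching, and 30 to 50% of patients with an early SAE; the documents give none of these. The tilt is smaller than the standard error of about 8 points and disappears at a hazard ratio of 1.

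A reader might go further and conclude that an effective UV1 would look less safe. The documents do not support that: it needs a material late SAE rate, equal hazards and an effect near 0.60 together, and chance variation could hide the tilt. This is a cheap improvement to the analysis, not a flaw that undermines the trial.

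**What to change.** In Section 9.4.3 and the SAP, before unblinding, keep the crude percentages and add:

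- **(a)** SAE percentages from first dose to 30 days after the last induction dose, with a note that this period includes the 9-day UV1-only lead-in in the experimental arm and is shorter for patients who stop induction early.
- **(b)** For SAEs after that period, exposure-adjusted rates per arm, with observation time ending at the protocol's own SAE cut-off. Do not pool both periods into one rate, because that over-corrects when SAEs cluster early.
- **(c)** As a supplement, cumulative incidence of first SAE with new anticancer treatment and death as competing events, and SAE observation time per arm beside the SAE tables. The curve shows timing and handles unequal follow-up to the cut-off, but it still reflects when patients switch, so it does not replace (b).

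The non-serious AE summary needs no change on this account. The inputs are already collected: SAE reports, and new anticancer treatments recorded in the eCRF under Section 6.2.3. The cost is some SAP wording and a few extra tables, with no change to trial conduct.
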